# 2. INTRODUCTION

ALXN1840 (bis-choline tetrathiomolybdate; formerly known as WTX101) is a novel, first-in-class, copper (Cu)-protein binding agent in development for the treatment of Wilson disease (WD) and primary biliary cholangitis (PBC).

# 2.1. Study Rationale

This study is being conducted to determine the effect of ALXN1840 at a single dose of 60 mg on the metabolism of celecoxib, a sensitive cytochrome P450 2C9 (CYP2C9) substrate, at a single dose of 200 mg (Celebrex®). ALXN1840 is considered to have the potential for weak to moderate drug-drug interactions (DDI) due to inhibition of CYP2C9, according to in vitro studies conducted using human liver microsomes and simulations performed to assess DDI risks (Study CYP0840-R2, Study 1907124 and Study AXP/1/B). This study has been designed and will be conducted in accordance with the current regulatory guidance issued by the US Food and Drug Administration (FDA) "Clinical Drug Interaction Studies — Cytochrome P450 Enzyme-and Transporter-Mediated Drug Interactions" (2020), European Medicines Agency (EMA) Committee for Medicinal Products for Human Use "Guideline on the Investigation of Drug Interaction" (2012), and the Japan Pharmaceuticals and Medical Devices Agency (PMDA) "Guideline on drug interaction for drug development" (2019).

Based on a mean ALXN1840 maximum observed plasma concentration (Cmax) value of 3.92 µM with a single dose of 60 mg enteric-coated (EC) tablet under fasting conditions in healthy participants (Study WTX101-102), a steady state plasma total Mo Cmax of 13.03 µM can be estimated, considering accumulation ratio of 3.33 with linear pharmacokinetics (PK). In the Phase 2 Study WTX101-201, conducted in patients with WD, the observed highest plasma total molybdenum (Mo) concentration was 20.3 µM after repeated doing of ALXN1840 at 60 mg; the dose was escalated to 120 mg at Week 4. Assuming all tetrathiomolybdate (the active ingredient in ALXN1840) in human plasma is free (a conservative approximation since 90% - 95% of the total Mo in plasma is bound to copper and albumin by forming tripartite complexes), there is no potential that ALXN1840 may induce cytochrome P450 (CYP) isoforms or inhibit p-glycoprotein, breast cancer resistance protein, or the organic anion and organic cation uptake transporters. However, as the estimated in vivo steady-state plasma levels of total Mo after dosing ALXN1840 at 60 mg (13.03  $\mu$ M) daily may exceed the drug concentration required to produce 50% of the maximal inhibition (IC50 value =  $6.9 \mu$ M) of CYP2C9 in vitro, a moderate potential for inhibition of CYP2C9 was theoretically and conservatively anticipated (Study 030519b, Study 030709c, Study MC05063, and Study CYP0840-R2).

Subsequent in vitro studies in human liver microsomes (HLM) have shown a potential inhibitory effect (competitive and time-dependent) of ALXN1840 (and possibly its degradation products) on CYP2C9-mediated metabolism (Study CYP0840-R2 and Study 1907124). The IC50 value for the inhibitory effect on CYP2C9 was observed at 6.9  $\mu$ M (3.0  $\mu$ g/mL) with the estimated Ki values of 6.07  $\mu$ M (2.6  $\mu$ g/mL; Study CYP0840-R2 and Study AXP/1/B). Furthermore, the study (Study 1907124) specifically examining the inactivation potential of ALXN1840 on CYP2C9 catalytic activity in vitro using HLM and the FDA recommended CYP2C9 probe substrate diclofenac 4'-hydroxylation with the time-dependent probe inhibitor tienilic acid as active control (US Food and Drug Administration), demonstrated potential for time-dependent inhibition (TDI)

at ALXN1840 concentrations  $\geq 30 \ \mu$ M. Because the maximum observed plasma total Mo concentration in the Phase 2 Study WTX101-201, conducted in patients with WD, was 20.3  $\mu$ M after repeated doing of ALXN1840 at 60 mg and then dose-escalated to 120 mg at Week 4, the observed in vitro TDI potential at ALXN1840 concentration of  $\geq 30 \ \mu$ M is not anticipated in vivo, even considering total Mo of 20.3  $\mu$ M is 100% active and free ALXN1840 (a most conservative case). Assuming 10% of the total Mo is in the form of free and active ALXN1840, which is still conservative given that most of this 10% are likely ALXN1840 degradants such as molybdate, then the highest anticipated individual free and active ALXN1840 concentration is at 2.03  $\mu$ M in patients with WD, when dosed at 120 mg daily at steady state. Overall, this, implies a negligible possibility for observing in vivo TDI with repeated daily doses of ALXN1840 at 60 mg or up to 120 mg in patients with WD.

Finally, a validated Simcyp® physiologically based pharmacokinetic model, developed using data from Study WTX101-HV-106, predicted a weak CYP2C9 inhibition potential for simulations of single dose ALXN1840 exposures at 120 or 240 mg. The predicted geometric mean of the AUC ratio of celecoxib was 1.5 for the highest simulated single dose of 240 mg ALXN1840 (Study AXP/1/B), indicating weak inhibitory potential in vivo (weak for AUC ratio of  $\geq 1.25$ - to < 2-fold), per the 2020 FDA guidance on "Clinical Drug Interaction Studies — Cytochrome P450 Enzyme- and Transporter-Mediated Drug Interactions". For the highest simulated single dose of 240 mg ALXN1840, the maximum in vivo estimated free plasma concentration available to interact with CYP2C9 is estimated at 4.1  $\mu$ M, after accounting for the formation of tetrathiomolybdate-Cu-albumin tripartite complexes (TPC), which is higher than the 2.03  $\mu$ M noted above.

Overall, based on in vitro and in silico study results, the maximum total daily doses in clinical studies (currently 60 mg in Phase 3 Study WTX101-301, but previously up to 120 mg in Phase 2 Study WTX101-201) are not anticipated to reach steady-state ALXN1840 concentrations associated with TDI. According to the FDA guidance (US FDA "Clinical Drug Interaction Studies - Cytochrome P450 Enzyme - and Transporter-Mediated Drug Interactions" [2020]), a single dose study design using the highest anticipated clinically relevant dose will be appropriate and justified if there is no TDI. Therefore, single dose of ALXN1840 at 60 mg, which is the highest allowed dose in the on-going Phase 3 Study WTX101-301 conducted for treating patients with WD, is justified to be tested as a potential perpetrator for the CYP2C9 metabolism of a sensitive substrate celecoxib.

CYP2C9 is the most abundant drug metabolizing cytochrome P450 2C subfamily enzyme in the human liver, and accounts for approximately 20% of total hepatic P450 protein with mass spectrometry quantitation. Common substrates of CYP2C9 include, but are not limited to, numerous NSAIDs, oral hypoglycemic agents, including tolbutamide and sulfonylureas, angiotensin II blockers, rifampicin and S-warfarin. In all, CYP2C9 covers the metabolism of approximately 15% of drugs that involve CYP450 enzymes (Daly, 2017; Dean, 2012).

The potentially weak to moderate inhibitory effects of a single 60 mg ALXN1840 dose on a single dose 200 mg celecoxib metabolism is anticipated to have a very limited safety concern based on the Celebrex® USPI (Celebrex®).

Further details of the currently available drug metabolism, pharmacokinetics, and safety data are available in the Investigator's Brochure (IB) for ALXN1840 (Edition 10, 25 Feb 2020).

# 2.2. Background

ALXN1840 is in development for the treatment of WD and PBC due to its improved stability properties over ammonium tetrathiomolybdate, the latter of which has previously been studied in patients with WD and other indications. Ammonium tetrathiomolybdate as well as bis-choline tetrathiomolybdate non-clinical and clinical data reported to date support therapeutic efficacy and with an appropriate safety profile for ALXN1840.

ALXN1840 rapidly forms irreversible TPC, which stabilize free and potentially toxic Cu leading to a reduction in the non-ceruloplasmin-bound Cu (NCC) concentrations or NCC corrected for TPC [NCCcorrected]) (Weiss, 2017).

Detailed descriptions of the chemistry, pharmacology, efficacy, and safety of ALXN1840 are provided in the IB for ALXN1840.

### 2.3. Benefit/Risk Assessment

More detailed information about the known and expected benefits and risks and reasonably expected adverse events (AEs) for ALXN1840 may be found in the IB and for celecoxib in the prescribing information (Celebrex®).

### 2.3.1. Risk Assessment

Details of the potential risks and mitigation strategy are provided in Table 2.

Potential Risk of Clinical Significance	Summary of Data/Rationale for Risk	Mitigation Strategy
ALXN1840		
Dose-dependent elevations in transaminases (ALT and AST)	Generally mild to moderate in severity, asymptomatic and reversible with dose adjustments were reported, usually after 3 – 6 weeks of treatment in patients with WD	Regular monitoring of liver function tests
Anemia	Anemia has been observed in patients with WD, PBC and cancer, and attributed to overtreatment and resultant Cu depletion	Monitoring complete blood count
Low white blood cell count (leukopenia, bone marrow toxicity)	Leukopenia and bone marrow toxicity (myelosuppression) have been observed in patients with WD and attributed to overtreatment and resultant Cu depletion	Monitoring complete blood count
Study Procedures	-	-
Risks associated with the study design and procedures	Participants will undergo repeated blood draws to measure the PK of the study intervention and metabolism. Blood draws may result in ecchymosis, redness and minor pain to the site. On rare	Blood draws are optimized for PK. A cannula may be placed to minimize needle sticks

Table 2:Potential Risks and Mitigation Strategy

	occasion, infection or thrombophlebitis can occur	
Celecoxib		
As per prescribing information	Celecoxib prescribing information (Celebrex®)	Participants will be monitored for adverse réactions and by regular laboratory assessments. Participants may be discontinued for significant drug related adverse events

Abbreviations: ALT = alanine aminotransferase; AST = aspartate aminotransferase; Cu = copper;

IB = Investigator's Brochure; PBC = primary biliary cholangitis; PK = pharmacokinetics;

WD = Wilson Disease.

#### 2.3.2. Benefit Assessment

This is a healthy volunteer study, and there is no direct benefit to study participants.

#### 2.3.3. Overall Benefit: Risk Conclusion

Taking into account the measures implemented to minimize risk to participants, the potential risks identified in association with ALXN1840 and celecoxib are justified by the anticipated benefits that may be afforded to patients with WD and PBC.

# **3. OBJECTIVES AND ENDPOINTS**

Objectives	Endpoints
Primary	
• To determine the effect of ALXN1840 on the PK of celecoxib, a sensitive CYP2C9 substrate	
 
PK parameters of celecoxib (Cmax, area under the plasma concentration (AUC) versus time curve from time 0 to the last quantifiable concentration [AUCt], and AUC versus time curve from time 0 to infinity [AUC∞]) with and without the coadministration of ALXN1840
 

Secondary	

 
To determine the effect of ALXN1840 on the PK of plasma Mo with the coadministration of celecoxib
 
To determine the safety and tolerability of ALXN1840, with the coadministration of celecoxib
 
	
 
PK parameters for plasma total Mo (Cmax, AUCt, and AUC∞) with the coadministration of celecoxib
 
Safety assessed by incidence of treatment-emergent adverse events (TEAEs) and treatment-emergent serious adverse events (TESAEs), physical examination, vital signs measurements, clinical laboratory and 12-lead electrocardiogram (ECG) results
 

Abbreviations:  $AUC_{\infty}$  = area under the plasma concentration versus time curve from time 0 to infinity;  $AUC_t$  = area under the plasma concentration versus time curve from time 0 to the last quantifiable concentration;  $C_{max}$  = maximum observed plasma concentration of the drug; CYP2C9 = cytochrome P450 2C9; ECG = electrocardiogram; PK = pharmacokinetics; TEAE = treatment-emergent adverse event; TESAE = treatment-emergent serious adverse event.

# 4. STUDY DESIGN

### 4.1. Overall Design

The study is being conducted as a randomized, 2-period, 2-sequence, cross-over study to determine the effect of a single dose of ALXN1840 (perpetrator) on the single dose celecoxib (victim) kinetics in healthy male and female participants.

The study has a Screening period (Day -28 to Day -2), two 11-day study periods (Day 1 to Day 11) with a minimum of 14 days between doses of celecoxib, and an End of Study (EOS) Visit (Day  $15 \pm 2$  days) after Period 2 dosing. Participants will report to the clinical research unit (CRU) on the day prior (Day -1) to both dosing periods.

All participants will receive 1 treatment in each study period; treatment order will be defined based on randomization:

- Treatment A: One 200 mg celecoxib capsule with 240 mL water (fasting).
- **Treatment B**: One 200 mg celecoxib capsule + 4 × 15 mg ALXN1840 EC tablets with 240 mL water (fasting).

Based on randomization, participants will be administered either Treatment A or Treatment B in each period. A wash-out period of at least 14 days must separate dose administration in Period 1 and Period 2. Participants will remain institutionalized from the day prior to dosing until Day 11 following dose administration for each period.

The PK profile of ALXN1840 and celecoxib will be determined by blood sampling following single dose administration over approximately 5 half-lives or more for both study interventions. Blood sampling for PK assessments will occur at pre-dose, 1, 2, 3, 4, 5, 6, 8, 12, 24, 48, 72, 96, 120, 144, 168, 192, 216, 240, and 336 hours post-dose to ensure full assessment of exposure over time. The nominal 336-hour sample for Period 1 is pre-dose sample for Period 2. In addition to PK sampling, safety and tolerability will be assessed by monitoring AEs, vital signs, 12-lead electrocardiograms (ECGs), and laboratory parameters.

Following scheduled procedures on Day 11, participants will be discharged from the unit. If there are any participants with clinically significant abnormalities at the time of discharge, the Investigator should notify the Medical Monitor prior to discharge, and participants may be asked to remain institutionalized for further clinical monitoring.

Participants may be asked or required to stay in the CRU between Periods 1 and 2, and/or before the EOS visit, for their own safety, and also to maintain the integrity of the conduct of the study.

The End of Study (EOS) Visit will occur approximately 4 days after discharge from Period 2, after collection of the nominal 336-hour PK sample.

This study will include approximately 38 participants; the overall study population will include a minimum of 40% of each sex.

Participants will be randomized to one of two sequences as described in Table 3.

Table 3:	Study Design
----------	--------------

Sequence	Treatment Sequence		Male a	Female a	Total
Number	Study Period 1	Study Period 2			
1	A	В	8 to 11	8 to 11	19
2	В	А	8 to 11	8 to 11	19
Total			16 to 22	16 to 22	38

aIn an effort to achieve balance between males and females in each sequence, there will be no less than 16 and no more than 22 of either sex (ie, a maximum split in either direction of approximately 60%:40%). Randomization will be stratified by sex.

Treatment A -One 200 mg celecoxib capsule with 240 mL water (fasting)

Treatment B – One 200 mg celecoxib capsule +  $4 \times 15$  mg ALXN1840 enteric-coated tablets with 240 mL water (fasting)

At the Investigator's discretion, additional participants may be screened to allow for a full enrollment of the study, with a minimum of 40% for each sex. Therefore, it is possible that all eligible participants may not be included. Participants not included in the study will be discharged without dosing on Day 1.

### 4.2. Scientific Rationale for Study Design

This study is being conducted in healthy participants so that the assessments are not confounded by disease activity, comorbidities, or concomitant medications. The inclusion and exclusion criteria for this study are consistent with Phase 1 clinical pharmacology studies that assess the medication of interest and to minimize assignment bias.

A 2-way crossover study design was adopted to control the variability within and between participants. Given the desire to evaluate the impact of sequence of administration, the study is being conducted as a 2-sequence, 2-period cross-over study. Blood sampling for PK assessment will include measures for ALXN1840 and celecoxib. Blood sampling timepoints support evaluation of time to reach maximum observed plasma concentration ( $T_{max}$ ) and  $C_{max}$  and include a minimum of 5 half-lives between each study intervention.

The interval between dose administration in each period will be at least 14 days, based on the estimated mean half-life for ALXN1840 of approximately 2 days as previously reported in the bioavailability studies (Studies WTX101-101 and WTX101-102), where healthy participants took an oral dose at 60 mg. Therefore, a minimum of 14 days between dose administration is considered sufficient to eliminate, on average, approximately more than 99.2% of the plasma total Mo before a second dose of celecoxib. The approximately 4-day interval after Period 2 dose administration will also ensure that the participants will have eliminated measurable concentrations of ALXN1840 at the EOS Visit regardless of the randomized dosing sequence. The mean elimination half-life ( $\pm$ SD) of celecoxib after chronic dosing is 11.2 ( $\pm$  3.5) hours (Celebrex®), therefore a minimum of 14-day interval between single dose administrations is sufficient to eliminate greater than 99.2% of plasma celecoxib.

# 4.3. Justification for Dose

### ALXN1840

The maximum tolerated dose (MTD) of ALXN1840 is unknown. To date, the 60 mg single dose and repeated daily doses have shown a good safety profile and were well tolerated throughout

the Phase 1 to Phase 3 clinical studies. The 60 mg dose is well within the dose range demonstrated to have a good safety profile in studies in healthy volunteers and patients with WD. The 60 mg dose is well within the dose range to have an acceptable safety profile in humans as demonstrated in the completed bioavailability studies that were conducted in healthy male and female participants (Study WTX101-101 and Study WTX101-102) with a median (range) body weight of 80.8 kg (57.6 to 107.0 kg) as well as the completed Study WTX101-201, conducted in patients with WD.

Tetrathiomolybdate reacts with albumin-bound Cu in the liver or blood to form a stable tripartite complex which is excreted into the bile. Tetrathiomolybdate which does not bind to Cu and albumin, is not metabolized by the liver but undergoes hydrolysis to form molybdate anion, which is excreted in the urine. Therefore, findings from the human microsome study (Study CYP0840-R2) are considered an over-estimation of the effect to be observed in vivo. Given that in vitro inhibition was observed with the ALXN1840 parent drug and no apparent accumulation of free ALXN1840 as part of the plasma ultrafiltrate (PUF) Mo or non-TPC-bound Mo after ALXN1840 repeated dosing (preliminary results from Study WTX101-201), a single dose of ALXN1840 is considered to be sufficient to assess the inhibition potential of CYP2C9 using celecoxib as the substrate. Single dose administration of the ALXN1840 tablet under fasted conditions resulted in a peak drug concentration of total Mo at approximately 4.54 hours, with a half-life of approximately 51 hours (Study WTX101-102).

### Celecoxib

Peak plasma levels of celecoxib occur approximately 3 hours after an oral dose under fasting conditions. Absolute bioavailability studies have not been conducted for this drug. Celecoxib exhibits a dose proportional increase in exposure after oral administration up to 200 mg twice daily and less than proportional increase at higher doses. It has extensive distribution and high protein binding with a half-life of approximately 11 hours (Celebrex®).

Celecoxib metabolism is predominantly mediated via CYP2C9 in the liver. Concomitant administration of fluconazole 200 mg and celecoxib 200 mg resulted in a 2-fold increase in celecoxib plasma concentration. This increase is due to the inhibition of celecoxib metabolism via CYP2C9 by fluconazole. For celecoxib, the selected dose in this study is 200 mg, which has been selected based on the drug interaction study with fluconazole in the Celebrex® US package insert (Celebrex®) and Diflucan® USPI (Diflucan®). A single dose is considered appropriate due to the linear PK of celecoxib within the approved therapeutic dose range.

Celecoxib is formulated into capsules at 50, 100, 200, and 400 mg dose strengths. Celecoxib may be administered initially up to a dose of 400 mg twice daily with adequate safety and tolerability. The dose of 200 mg represents the highest dose within the linear range of the drug to allow DDI assessment (linear PK is thought to be limited by poor absorption above 200 mg). Even though ALXN1840 is considered theoretically and conservatively to have potential for moderate inhibition of CYP2C9 in vitro, because this study is being conducted as a single dose study, without risk of accumulation, no dose adjustment is being made to the dose of celecoxib. A dose of 200 mg is not expected to result in sufficiently high exposure to cause an increase in safety risk.

# 4.4. End of Study Definition

A participant is considered to have completed the study if he/she has completed all phases of the study including the last scheduled procedure shown in the Schedule of Activities (SoA).

The end of the study is defined as the date the last participant completes the last visit as shown in the SoA (Table 1).

# 5. STUDY POPULATION

Prospective approval of protocol deviations to recruitment and enrollment criteria, also known as protocol waivers or exemptions, is not permitted.

### 5.1. Inclusion Criteria

Participants are eligible to be included in the study only if all of the following criteria apply:

### Age

1. Participants must be 18 to 50 years of age inclusive, at the time of signing the informed consent.

### Type of Participant and Disease Characteristics

- 2. Participants who are healthy as determined by medical evaluation including medical history, physical examination, vital signs, 12-lead ECG, and clinical laboratory evaluation (hematology, biochemistry, coagulation, and urinalysis) that are reasonably likely to interfere with the participant's participation in or ability to complete the study, or to potentially confound interpretation of study results, as assessed by the Investigator.
- 3. Adequate venous access in the left or right arm to allow collection of a number of blood samples.

### Weight

4. Body weight  $\ge 45$  to  $\le 100$  kg and body mass index (BMI) within the range of 18 to < 30 kg/m^2 at Screening.

#### Sex

- 5. Contraceptive use by men or women should be consistent with local regulations regarding the methods of contraception for those participating in clinical studies.
  - a. Male Participants:
  - Male participants, if heterosexually active with a female spouse or partner of childbearing potential or a pregnant or breastfeeding spouse or partner, must agree to use barrier contraception (male condom) for the duration of the study and for at least 3 months after the end of systemic exposure of the study intervention (ie, 3 months after the EOS Visit). Male participants must also agree to not donate sperm for at least 3 months after the end of systemic exposure of the study intervention (ie, 3 months after the EOS Visit).
  - Female spouses or partners of male participants who are of childbearing potential must use highly effective contraception as defined below and in Section 10.4, starting at least 1 menstrual cycle before (the male participant's) first study intervention administration and continuing until at least 3 months after the end of their male partner's systemic exposure to the study intervention (ie, 3 months after the EOS Visit).
  - Barrier contraception is required even with documented medical assessment of surgical success of a vasectomy. For male participants who have had a vasectomy

(with documented evidence of azoospermia if possible) and agree to use a barrier method (male condom) for the stated time period, no additional contraceptive method is required by their female partner.

- b. Female Participants:
- Female participants or female partners of male participants of childbearing potential, (including breastfeeding females), if heterosexually active, must be willing to follow protocol-specified contraception guidance starting at least 1 menstrual cycle before first study intervention administration and continuing for at least 3 months after the end of systemic exposure of the study intervention (ie, 3 months after the EOS Visit). Female participants must not donate ova for at least 3 months after the EOS (ie, 3 months after the EOS Visit).
- Female participants who are documented as being of non-childbearing potential as defined in Section 10.4 are exempt from contraception requirements.
- Highly effective contraceptive methods for female participants and female partners of male participants are described in Section 10.4.
- Women of childbearing potential must have a negative highly sensitive serum pregnancy test at screening. Additional urine pregnancy testing will be standard for the protocol unless serum testing is required by site policies, local regulation, or IRB/IEC and should be performed per the time points specified in the SoA (Table 1).

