### 5.2. Exclusion Criteria

Participants are excluded from the study if any of the following criteria apply:

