#### **Events Not Meeting the AE Definition**

- Medical or surgical procedure (eg, endoscopy, appendectomy): The condition that leads to the procedure is the AE. Situations in which an untoward medical occurrence did not occur (eg, hospitalization for elective surgery if planned before the signing the ICF, admissions for social reasons or for convenience).
- Anticipated day-to-day fluctuations of pre-existing disease(s) or condition(s) present or detected at the start of the study that do not worsen.
- A medication error (including intentional misuse, abuse, and overdose of the product) or use other than what is defined in the protocol is not considered an AE unless there is an untoward medical occurrence as a result of a medication error.
- Cases of pregnancy that occur during maternal or paternal exposure to study intervention are to be reported within 24 hours of Investigator/site awareness. Data on fetal outcome and breastfeeding will be collected for regulatory reporting and safety evaluation.
- Situations in which an untoward medical occurrence did not occur (social and/or convenience admission to a hospital).

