  - If a female participant or a male participant's female spouse/partner becomes pregnant during the conduct of this study, the Investigator must submit the "Pregnancy/Breastfeeding Reporting and Outcome Form" to Alexion Global Drug Safety (GDS) via fax or email (see Section 10.3 [Appendix 3] for contact information). When the outcome of the pregnancy becomes known, the form should be updated and submitted to Alexion GDS. If additional follow up is required, the Investigator will be requested to provide the information.
  - Exposure of an infant to an Alexion product during breastfeeding must also be reported (via the "Pregnancy/Breastfeeding Reporting and Outcome Form") and any AEs experienced by the infant must be reported to Alexion GDS or designee via email or facsimile (see Section 10.3 for contact information).

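### No criterion bars breastfeeding women or restricts nursing or expressed milk, and the one mention of them in inclusion 5b is ambiguous

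*Protocol*

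**What the plan says.** Breastfeeding participants come up in the Protocol only indirectly.

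- **Section 5.1, criterion 5b**, under the Female Participants sub-heading, names the people who must follow the contraception guidance: "Female participants or female partners of male participants of childbearing potential, (including breastfeeding females), if heterosexually active". It sets a contraception duty and says nothing else about nursing.
- **Section 5.1, criterion 5b**, also gives the only reproductive screen: "Women of childbearing potential must have a negative highly sensitive serum pregnancy test at screening". Further pregnancy tests follow at the times in Table 1.
- **Section 5.2** opens with "Participants are excluded from the study if any of the following criteria apply" and lists criteria 1 to 22. None mentions breastfeeding, lactation or nursing.
- **Section 10.4** contains the rule on infants: "Exposure of an infant to an Alexion product during breastfeeding must also be reported". The same sentence requires the infant's adverse events to be reported to the sponsor.
- **Section 10.3.1**, in the item on pregnancies during exposure, adds: "Data on fetal outcome and breastfeeding will be collected for regulatory reporting and safety evaluation".
- **Section 2.3.2** states: "This is a healthy volunteer study, and there is no direct benefit to study participants".
- **Section 4.1** states: "All participants will receive 1 treatment in each study period; treatment order will be defined based on randomization". Each participant who completes the study therefore takes celecoxib twice and ALXN1840 once. She stays in the unit from Day -1 to Day 11 of each period.

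**The concern.** Whether a breastfeeding woman may be dosed is an eligibility question, and the protocol should answer it. At present a site that follows Section 5 to the letter has no ground for refusing a healthy woman who is breastfeeding, and no instruction to give her about nursing or expressed milk.

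The party at risk is an infant who is not a participant. Section 2.3 weighs risk to participants against anticipated benefit to patients with Wilson disease or primary biliary cholangitis, and does not mention an infant. Section 10.4 foresees that an infant might be exposed, but it acts only after the event. On its wording it covers the sponsor's product. Celecoxib is supplied by the site (Table 5) and taken in both periods, and it has no matching rule on infant exposure.

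The study question does not depend on enrolling breastfeeding women, so the risk is avoidable.

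**Working it through.** There is no stated figure to reproduce. The check is a reading of the eligibility text, followed by a small calculation of the exposure window.

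**Step 1: is there any bar?**

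- Inclusion criteria 1 to 6: none requires that a participant is not breastfeeding. Criterion 2 concerns health findings that could interfere with participation or confound results, and lactation is not an illness.
- Exclusion criteria 1 to 22: no mention. Criterion 21 covers sensitivity and allergy only.
- Table 4 (lifestyle): no instruction to stop nursing or to discard milk.
- Screening: a pregnancy test does not detect lactation.
- SAP: section 8.6.3 covers pregnancy tests only and adds no restriction.

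**Step 2: does the reading of 5b matter?** The parenthesis follows the words on partners, and criterion 5a already speaks of a breastfeeding partner, which supports the partner reading. It also sits under Female Participants, in a sentence whose subject begins with female participants, which supports the participant reading. On the first reading, 5b is silent about breastfeeding participants and nothing else excludes them. On the second, 5b presupposes that they can enrol. She is eligible either way.

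**Step 3: how much drug is left, and when?** The inputs are the total Mo half-life of about 51 h (Section 4.3), the celecoxib half-life of 11.2 ± 3.5 h (Section 4.2), and discharge on Day 11, nominally 240 h after dosing (Table 1). The fraction remaining in maternal plasma is 2^(−t / half-life), taken as simple exponential decay from dosing.

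| Hours after dose | Total Mo, 51 h | Celecoxib, 11.2 h |
|---|---|---|
| 24 | 72% | 23% |
| 72 | 38% | 1.2% |
| 120 | 20% | 0.06% |
| 240 (Day 11) | 3.8% | under 0.0001% |
| 336 | 1.0% | nil |

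For discharge, 240/51 = 4.71 half-lives and 2^(−4.71) = 3.8%. With the rounded half-life of 2 days (48 h), 240/48 = 5 and 2^(−5) = 3.1%. For celecoxib at one SD above the mean half-life (14.7 h), 2^(−240/14.7) is about 0.001%.

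Almost all of the period with appreciable levels therefore falls inside confinement. After discharge a small residue of Mo remains.

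**Step 4: what cannot be computed.** These are maternal plasma fractions. The documents give no figure for transfer into milk. Section 2.1 says that 90% to 95% of total Mo in plasma is bound to copper and albumin, so total Mo is not a measure of free active drug. No infant dose follows from these inputs.

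**The case against.** The strongest reply has four parts.

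1. **Confinement already protects the infant.** From Day -1 to Day 11 the participant is in the unit, possibly longer, so ordinary nursing is unlikely while levels are high. This stands, and it is the main reason why the practical risk is small. It does not close the gap: confinement is not described as an infant safeguard, and it does not address expressed milk.

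2. **Criterion 5b does not admit breastfeeding women.** A reader might infer from the parenthesis that the protocol deliberately enrols them. The text does not support that, because the sentence sets a contraception duty and the parenthesis may refer to partners. The point rests on the missing exclusion, not on 5b as a grant of eligibility.

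3. **There is infant follow-up, and other documents may cover the rest.** A reader might infer that the infant has no safety follow-up at all, or that consent ignores the matter. The first is wrong, since Section 10.4 requires infant adverse events to be reported. The second cannot be checked. Inclusion 6 binds participants to restrictions in the consent form, which is not available here, and Section 2.3 refers to the Investigator's Brochure and the celecoxib labelling for detail. An eligibility rule still belongs in Section 5.

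4. **Sections 5.1, 10.3 and 10.4 do not contradict each other.** This is fair. Contraception applies, and exposure is reported if it occurs. The defect is an omission and an ambiguous phrase, not a conflict.

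**Conclusion.** The point holds as a gap in eligibility. A breastfeeding woman can be enrolled and dosed under the protocol as written, nursing and expressed milk are not addressed, and infant risk is not assessed in a trial without direct benefit to participants.

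Its size is modest. Table 3 plans 16 to 22 women. The documents do not say how many might be breastfeeding; none to a few is an assumption. About 3.8% of maternal plasma total Mo remains at Day 11 discharge (3.1% on a 48-hour half-life), and celecoxib is essentially gone.

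A reader might point to the roughly 27% of total Mo left four days after dosing (2^(−96/51)) and infer that an infant would be exposed for days. That does not follow: four days falls inside confinement, and the figure describes total Mo in the mother's plasma, not drug in milk or in the infant.

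Nothing here affects the primary PK comparison, the sample size or the analysis. The right label is a cheap improvement.

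**What to change.** Add breastfeeding to the exclusion criteria in Section 5.2. Reword criterion 5b in Section 5.1 so that the parenthesis applies only to partners of male participants.

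If the sponsor does intend to enrol breastfeeding women, the protocol should say so. Section 2.3 should then assess infant risk for both drugs, and 5.1, 5.2 and 10.4 should be reconciled so that the terms of participation are explicit. That includes whether the reporting rule in 10.4 extends to celecoxib.

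The cost is one added line and one rewording, made by amendment. The downside is that a few otherwise eligible women may be excluded, which should have a negligible effect on recruiting 16 to 22 women.
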